### **Exclusion Criteria**

1. Currently in an intensive care unit
2. Physician declines to provide consent
3. Patient unable to provide consent (e.g., history of cognitive impairment, unable to understand English) or declines to provide consent

For our study regarding correlation of the Koko with the SpiroPD devices to measure lung function, we will have power to detect a small to moderate effect size ( $p=0.023$ ) at  $>80\%$  ( $87\%$ ) power with  $n=150$  participants at an alpha  $<0.05$ .

Statistical Test (Spearman)	Sample Size	Power	Correlation	Significance Level
Correlation	193.78	0.8	0.2	0.05
Correlation	145.92	0.8	0.23	0.05
Correlation	123.13	0.8	0.25	0.05
Correlation	84.75	0.8	0.3	0.05

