## **TYPE AND NUMBER OF EXPERIMENTAL SUBJECTS**

We will enroll 150 study participants.

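### The power sentence contradicts its own table: at n=150 a correlation of 0.23 gives about 81% power, not 87%, and the printed 0.023 gives about 6%

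*Combined protocol and SAP*

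**What the plan says.** The section on type and number of subjects sets the size of the study: "We will enroll 150 study participants". The justification comes after the list of exclusion criteria, without a heading of its own. It says that "we will have power to detect a small to moderate effect size ( $p=0.023", gives the power as above 80% and specifically 87%, and sets the error rate with "participants at an alpha $<0.05".

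The table beneath is labelled as a Spearman test and lists the sample size needed for 80% power at a significance level of 0.05. It has four rows: 193.78 for a correlation of 0.20, 145.92 for 0.23, 123.13 for 0.25 and 84.75 for 0.30. The two rows that matter here read "Correlation 145.92 0.8 0.23 0.05" and "Correlation 123.13 0.8 0.25 0.05" (columns: test, sample size, power, correlation, significance level). The table has no row for 0.023, for n=150 or for 87% power. Neither the sentence nor the table says whether the test is one- or two-sided.

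**The concern.** A correlation of 0.023 is practically zero. It cannot be called small to moderate, and 150 participants could not detect it with useful power. The obvious reading is a misplaced decimal for the 0.23 in the table.

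That reading does not rescue the sentence. The table puts 80% power for 0.23 at 145.92 participants, and about four more cannot add seven points of power. So either the effect size is wrong by more than a decimal place, or the 87% is wrong, or the sentence was calculated on a different basis from the table.

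This is the document's only statement of what 150 participants can detect. A reader who relies on it, or who corrects only the decimal, takes away a wrong figure.

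**Working it through.** **Inputs.** n = 150 (type and number of subjects; power sentence). Alpha = 0.05, effect 0.023 and power 87% (power sentence). Four pairs of correlation and sample size at 80% power (table). The null hypothesis is taken as zero correlation, which is what the table's figures imply.

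**Formula.** With t the critical value on n − 2 degrees of freedom (two-sided 5%):

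- rc = t / √(t² + n − 2)
- zr = atanh(r) + r / (2(n − 1))
- zc = atanh(rc) + rc / (2(n − 1))
- power = Φ((zr − zc)√(n − 3)) + Φ((−zr − zc)√(n − 3))

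**Step 1: reproduce the table.** Solving for the n that gives 80% power:

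| Correlation | Table | Two-sided | One-sided |
|---|---|---|---|
| 0.20 | 193.78 | 193.776 | 153.07 |
| 0.23 | 145.92 | 145.922 | 115.37 |
| 0.25 | 123.13 | 123.130 | 97.42 |
| 0.30 | 84.75 | 84.749 | 67.19 |

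The two-sided version matches every row to two decimals and the one-sided version matches none. The table is therefore two-sided.

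**Step 2: power at n = 150 by the same formula.** Here t = 1.9761, rc = 0.1603, zc = 0.1623 and √(n − 3) = √147 = 12.124.

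- r = 0.023: zr = 0.0231. Power = Φ(−1.688) + Φ(−2.247) = 0.0457 + 0.0123 = **5.8%**.
- r = 0.23: zr = 0.2350. Power = Φ(0.881) = **81.1%** (the second tail is negligible).
- r = 0.25: zr = 0.2563. Power = Φ(1.139) = **87.3%**.

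For 0.23, power is 80.0% at n = 145.92 and 81.1% at n = 150, a gain of 1.1 points.

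**Step 3: what 87% would need.** At n = 150, power that rounds to 87% needs a correlation between 0.247 and 0.251 (0.249 for exactly 87%). At a correlation of 0.23, 87% power needs about 176 participants. At 0.023, even 80% power would need about 14,800.

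**Step 4: does another approximation give 87%?** At n = 150, two-sided:

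| Method | r = 0.023 | r = 0.23 | r = 0.25 |
|---|---|---|---|
| Table's formula | 5.8% | 81.1% | 87.3% |
| Plain Fisher z | 5.9% | 81.0% | 87.2% |
| Fisher z, variance × 1.06 for Spearman (assumed; not in the documents) | 5.8% | 78.8% | 85.3% |

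For 0.23, the noncentral t gives 82.0%. A simulation of 50,000 bivariate normal samples gives 81.1% for Pearson and 77.2% for Spearman. The two-sided results for 0.23 therefore run from 77.2% to 82.0%, and none reaches 87%.

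**The case against.** Five points can be made for the sentence.

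- **The intended effect is not known to be 0.23.** The sentence never prints 0.23, and 87% fits the table's 0.25 case. The effect size may be the only wrong figure. This stands: the 6-point overstatement is conditional on 0.23 being meant. What is certain is that the printed pair is inconsistent.
- **The 87% may be one-sided.** A one-sided 5% test at 0.23 gives 88.5% by the table's formula, and 86.7% by plain Fisher z with the 1.06 factor, which rounds to 87%. A one-sided origin cannot be excluded. It would leave a one-sided sentence above a two-sided table with nothing to tell the reader so, and it does nothing for 0.023.
- **The 6% is of no practical interest,** because nobody designed for 0.023. That is fair. The figure only shows that the printed value cannot be meant. The printed letter p may also be a rho lost when the PDF was read, and nothing here rests on it.
- **Little depends on it.** Power above 80% does hold for 0.23 by the table's method, and no study decision turns on 81% against 87%. This stands and limits the weight of the point.
- **81% may itself be optimistic for Spearman.** The table's formula makes no Spearman adjustment; with the assumed 1.06 factor, power at 0.23 is 78.8%. This also stands, so the restated figure should be tied to the table's method.

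**Conclusion.** The concern holds. An effect of 0.023 with 87% power at n=150 is impossible under every method tried, and no other part of the document corrects it. By the method that reproduces the table, the power is 5.8% as printed and 81.1% if 0.23 was meant; 87% belongs to a correlation of about 0.25. Correcting the decimal alone leaves power overstated by about 6 points (87% against 81%).

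This rests on a two-sided alpha of 0.05, inferred from the table because the text does not state it, and on a null hypothesis of zero correlation. The origin of the 87% is unknown.

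The sample size is not in question. The 0.23 row needs 145.92, so 150 is consistent with it, and the Specific Aim 1 criterion in the Statistical Analyses section is unaffected. The sentence should be corrected, but the design can stand.

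**What to change.** Rewrite the power sentence as one consistent pair for n=150 and two-sided alpha 0.05, calculated by the table's method: either a correlation of 0.23 with 81% power, or a correlation of 0.25 with 87% power. State that the test is two-sided, and name the approximation so that the figure can be reproduced.

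The cost is one sentence. If 0.23 is kept, the stated power falls from 87% to 81%. If 87% is kept, the stated detectable correlation becomes 0.25. Enrolment and the planned analysis stay as they are.

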## STATISTICAL ANALYSES

**SA1:** Correlation between KoKo and SpiroPD measurements will be assessed using Spearman's correlation coefficient. A high correlation ( $> 0.8$ ) will demonstrate the usefulness of the SpiroPD device in these patients.

**SA2:** Feasibility process measures such as proportion of participants who adhere to the at-home use of SpiroPD lung function testing, adherence measures to treatment regimens, and estimates of efficacy as denoted by exacerbations and acute care utilization will be analyzed using descriptive statistics. Patient characteristic associated with increased SpiroPD use, treatment adherence, and efficacy of lung function testing will use McNemars, Fishers exact or Chi square testing for categorical variables and rank sum or t-tests for continuous variables.

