## BACKGROUND

Chronic Obstructive Pulmonary Disease (COPD) results in nearly 750,000 hospitalizations annually and is the third leading cause of “early” (within 30-day) hospital readmissions in the United States. Curbing preventable early readmissions for acute exacerbations of COPD (AECOPD) has become a national priority, as demonstrated by the Medicare Hospital Readmissions Reduction financial penalty program. One critical barrier in assessing readmission risk is the lack of an easily-measured ‘vital sign’ for COPD: accurate, timely measurements of lung function. Unlike other medical problems that have validated, easily-obtained measurements of organ function, COPD evaluation often defaults to patient report and physician evaluation without critical physiologic data. This lack of objective pulmonary function data during AECOPD in turn leads to critical errors in disease severity assessment. However, the required, repeated measurements by spirometry that can demonstrate responses to therapy can be time-consuming and expensive to perform in a laboratory, and both equipment and staffing infrastructure for bedside testing is cumbersome and often not prioritized. For these reasons, spirometry frequently is not done for patients with AECOPD.

To monitor patient responses to therapy and to assess risks based on objective measures, we propose to the study the use of a portable, patient-driven device (“SpiroPD”) that can be used in both in-patient and outpatient settings, and that reports (via the internet) values collected in real time. While the device has been used in the lung transplant community and for patients with cystic fibrosis, no studies have been done to validate its use in COPD. Our protocol involves in-hospital patient training with the device followed by serial measurements at home in the first 30 days post hospital-discharge.

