## PURPOSE & HYPOTHESIS

Our central hypotheses are that handheld spirometry is feasible for inpatient and at-home use and is equally efficacious at determining lung function when compared with bedside spirometry measurements. To test these hypotheses, we propose the following specific aims:

**Specific Aim 1:** Determine the correlation of SpiroPD handheld spirometry measurements with bedside Koko spirometry lung function.

**Hypothesis:** Correlation between the two lung function tests will be substantial for both hospitalized and ambulatory patients.

**Specific Aim 2:** To determine the feasibility, adherence, and preliminary management efficacy of home SpiroPD testing.

**Hypotheses:** (1) Patients will demonstrate substantial adherence to daily home spirometry testing; (2) medication adherence will increase significantly in patients who are adherent to daily home spirometry testing; (3) acute care utilization will decrease significantly in adherent patients.

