## METHODS OVERVIEW

We will enroll patients diagnosed with COPD both in the hospital and clinic setting and follow for 30 days. Participants will complete comparative lung function measurements with both devices while in the hospital or clinic at time of enrollment and at the 30-day follow up visit. Correlation will be assessed using Spearman's correlation coefficient. A high correlation ( $> 0.8$ ) will demonstrate the usefulness of the SpiroPD device in these patients in both settings. We will use the FDA-cleared (K 103575) SpiroPD device for its intended use.

At the time of their initial study visit, study participants will be given a SpiroPD device for use at home following instruction in the hospital or clinic. Patient adherence to daily testing over one-month will be monitored using real-time capture Wi-Fi-data from the SpiroPD data portal. Participant surveys will ascertain barriers and facilitators of daily spirometry lung function testing, and subject attitudes and beliefs about the usefulness of this testing for self-management. Adherence to medication use and utilization outcomes will be measured using patient logs. Acute care utilization will be measured via tracking of ED visits, hospitalizations, and urgent care calls. Information will be collected at the 30 day (+/- 1 week) visit through in-person (preferred) or phone call visits (if do not show for in person visit).

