### **Outpatient enrollment**

Patients being seen in the Pulmonary Clinic will be approached for participation following their clinic visit. As with the inpatient study, a trained research assistant will do a preliminary screening (wireless internet, vision) to see if the patient is eligible for the study. The research assistant will conduct obtain KoKo data from the clinical visit the patient just completed and SpiroPD spirometry with the participant. During this assessment, the research assistant will also provide the participant with training on use and function of the SpiroPD device. Outpatients will be offered a CTA/parking pass, if they decide to enroll but cannot complete the visit on the day of enrollment to return for the first visit. They will return for a research visit at 30 days (+/- 1 week) if no clinic visit is scheduled during the 30 day research visit window. The patient will be offered a CTA/bus pass to return for their 30 day follow up. If the study participant is unable to attend the study visit in-person, we will arrange a phone call.

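### The hypothesis is that SpiroPD performs equally to bedside spirometry, but the only device comparison is Spearman's rho > 0.8, which cannot see constant or proportional bias

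*Combined protocol and SAP*

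**What the plan says.** Purpose & Hypothesis puts forward the central hypothesis that handheld spirometry is feasible and "is equally efficacious at determining lung function when compared with bedside spirometry measurements". The specific aims are introduced as the means of testing it. Aim 1 is to "Determine the correlation of SpiroPD handheld spirometry measurements with bedside Koko spirometry lung function", with the hypothesis "Correlation between the two lung function tests will be substantial for both hospitalized and ambulatory patients".

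SA1 in Statistical Analyses gives the method: "Correlation between KoKo and SpiroPD measurements will be assessed using Spearman's correlation coefficient". A value above 0.8 "will demonstrate the usefulness of the SpiroPD device in these patients". Methods Overview has the same method and threshold, and there the result "will demonstrate the usefulness of the SpiroPD device in these patients in both settings".

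No section gives a mean difference, limits of agreement, a concordance or intraclass coefficient, a method-comparison regression or an acceptable difference between devices. The tests listed under SA2 concern patient characteristics, not the two devices. The spirometry parameter to be compared is not named.

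**The concern.** Equal performance in determining lung function is a statement about agreement: for the same patient, the two devices should give nearly the same value. A rank correlation asks only whether they put patients in the same order. That leaves three gaps.

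- A constant or positive proportional error in one device leaves Spearman's rho exactly where it was.
- Random error is bounded only loosely by rho > 0.8.
- For a given random error, rho depends on how widely lung function varies in the sample, so patient mix can decide whether the criterion is met.

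Background motivates the device partly by severity assessment: "This lack of objective pulmonary function data during AECOPD in turn leads to critical errors in disease severity assessment". Severity depends on the value, not on rank. Background also says the device has not been validated in COPD, and the results are meant to prepare further studies and grant applications. If the rule is followed as written, a conclusion of equal performance could be carried forward when the data do not support it.

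**Working it through.** **1. The plan's own figure.** The sample-size table, which follows Exclusion Criteria, gives 145.92 participants for 80% power at a correlation of 0.23 and alpha 0.05. A two-sided Fisher z test of zero correlation gives n = ((1.960 + 0.842)/atanh(0.23))² + 3 = 146.1, so the row reproduces. The calculation thus concerns whether the correlation differs from zero. It addresses neither the 0.8 criterion nor agreement.

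**2. Invariance.** Ranks do not change when readings are shifted by a constant or multiplied by a positive factor. In one simulated set of 150 pairs, rho was 0.9692. It stayed at 0.9692 after one device was shifted by −0.3 L, multiplied by 0.8, or changed to 0.5x − 0.2. The result needs no assumed mean or SD.

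**3. Random error allowed at rho = 0.8, with no bias.** Assuming bivariate normal readings:
- Pearson r = 2 sin(π × 0.8/6) = 0.813.
- SD of differences ÷ patient SD = √(2(1 − r)) = 0.611 if the devices have equal variance, or √(1/r² − 1) = 0.715 if all the error is in SpiroPD.
- Multiplied by 1.96, the limits of agreement are ±1.20 and ±1.40 patient SDs.

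The documents give no parameter or SD, so litres need an assumption. For FEV1 SDs of 0.4, 0.5 and 0.7 L the limits are ±0.48 to 0.56 L, ±0.60 to 0.70 L and ±0.84 to 0.98 L.

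**4. Hypothetical proportional bias.** This is a simulation of 400,000 pairs with KoKo normal (mean 1.3 L, SD 0.5 L, floored at 0.3 L) and SpiroPD = f × KoKo + noise of SD 0.1 L. All inputs are assumed.

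| SpiroPD reads | Spearman | Mean difference | Limits of agreement | Lin's concordance |
|---|---|---|---|---|
| 10% low | 0.974 | −0.13 L | −0.35 to 0.09 L | 0.94 |
| 20% low | 0.967 | −0.26 L | −0.53 to 0.01 L | 0.81 |
| 30% low | 0.957 | −0.39 L | −0.74 to −0.04 L | 0.65 |

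Rho slips slightly down the table only because the noise is held at 0.1 L while the signal shrinks. For 20% low with patient SDs of 0.4 to 0.7 L, rho is 0.95 to 0.98 and concordance 0.75 to 0.88.

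A second simulation used 1,000 trials of 150 pairs (mean 1.4 L, SD 0.5 L, error SD 0.1 L per device), with the bias applied to the whole SpiroPD reading. Rho averaged 0.955 and passed 0.8 in every trial, whether the device was unbiased, 0.3 L low (concordance 0.81), 20% low (0.78) or reading half the true value (0.30).

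**5. Dependence on patient spread.** Take an unbiased error of SD 0.3 L, so limits of ±1.96 × 0.3 = ±0.59 L throughout. Pearson r = SD/√(SD² + 0.09), and Spearman = (6/π) asin(r/2).
- Patient SD 0.4 L: 0.79, fails.
- Patient SD 0.5 L: 0.85, passes.
- Patient SD 0.7 L: 0.91, passes.

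**6. Precision of an agreement analysis.** The 95% CI half-width of each limit, in SDs of the differences, is 1.96 √(1/n + 1.96²/(2(n − 1))): 0.27 at n = 150, 0.39 at n = 75 and 0.48 at n = 50. The 75 and 50 are assumed sizes for one setting.

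**The case against.** Aim 1 and its hypothesis speak only of correlation, and the sample size is for a correlation, so at aim level the analysis matches the question. The threshold is said to show usefulness, not interchangeability. This is a single-centre pilot with an FDA-cleared device, and both devices' readings will be on file, so agreement could be computed later. Background also motivates the device by repeated measurement of response to therapy, where a constant offset matters less. The litre figures are illustrative, nothing in the documents suggests a 10 to 30% bias, and at 10% low concordance is still 0.94.

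Part of this stands. The mismatch is between the central hypothesis and the analysis, so narrowing the claim to association is a legitimate repair. Tracking change within a patient does tolerate a constant offset. The litre examples show what the rule would let through, not what is expected, and the limits at rho = 0.8 rest on bivariate normality.

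It does not remove the problem. The aims are offered as the test of the central hypothesis, which includes equal performance. Random error affects both absolute and within-patient use. Neither pilot status nor clearance supplies agreement evidence in COPD, which Background says is lacking. An agreement analysis chosen after the data are seen, with the acceptable difference set then, carries much less weight.

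**Conclusion.** The concern holds and should be fixed before the device comparison is analysed. As written, the sole criterion for comparing the devices can be met when the equal-performance hypothesis is false. Its blindness to constant and positive proportional bias is exact and rests on no assumption. With no bias at all, rho = 0.8 is compatible with limits of agreement of ±1.20 to ±1.40 patient SDs, given bivariate normality. Under the assumed FEV1 values, a device reading 20% low passes easily, at rho 0.97 with a mean difference of −0.26 L. The size of any real bias is unknown. The point is that the planned analysis would not reveal it.

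**What to change.** In SA1:
- Name the spirometry parameter or parameters.
- Make paired agreement the main analysis: mean difference and Bland-Altman 95% limits of agreement with confidence intervals, a check for proportional bias, and Lin's concordance or an absolute-agreement intraclass coefficient. Judge the result against an acceptable difference stated and justified in advance. Mean difference and limits against that difference are the essential part.
- Use one baseline pair per participant, and report overall and separately for inpatients and outpatients.
- Take same-day pairs as the main set. Outpatient KoKo values come from the clinic visit, and Outpatient enrollment provides for patients "if they decide to enroll but cannot complete the visit on the day of enrollment to return for the first visit". Flag different-day pairs or put them in a sensitivity analysis.
- Keep Spearman as secondary, and replace the usefulness sentence in SA1 and Methods Overview.

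If the analysis is left as it is, limit the claims in Purpose & Hypothesis, Methods Overview and SA1 to association between the devices.

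The cost is mainly text in those three sections, plus recording the date of each KoKo and SpiroPD test. The sample-size paragraph should be supplemented with the precision figures (±0.27 SD of the differences per limit at 150 pairs, about ±0.39 SD at 75), since a test of zero correlation does not justify an agreement analysis. The same-day rule may lose some outpatient pairs. The documents do not say how many, so the 150-pair precision is a best case. The headline may look less favourable than a high correlation.

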Demonstration in a pilot, single-center trial of the usefulness of real-time, repeated hand-held spirometry to provide objective measurements of lung function in AECOPD will have a substantial impact on both patient health outcomes and on health care utilization and will set the stage for appropriate next-step studies and NIH grant applications. It is unknown whether this specific technology will be acceptable in our population, though previous research suggests that older patients may be willing to use home monitoring technology. Our multi-disciplinary team includes providers from the Department of Medicine and the UCM COPD Readmissions Program team.

---

 Centers for Medicare & Medicaid Services. Readmissions Reduction Program. 2014. Available at: <http://www.cms.gov/Medicare/Medicare-Fee-for-Service-Payment/AcuteInpatientPPS/Readmissions-Reduction-Program.html>. Accessed January 14, 2015.

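### SA1 correlates the two devices' measurements only, so a Spearman coefficient above 0.8 could be reached by a device that follows within-patient change poorly, although monitoring response to therapy is the stated use

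*Combined protocol and SAP*

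**What the plan says.** The Background gives a longitudinal reason for the device. It values "repeated measurements by spirometry that can demonstrate responses to therapy", introduces SpiroPD "To monitor patient responses to therapy and to assess risks based on objective measures", and describes "serial measurements at home in the first 30 days post hospital-discharge". The pilot is meant to show the "usefulness of real-time, repeated hand-held spirometry to provide objective measurements of lung function in AECOPD".

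The device comparison is not longitudinal. Specific Aim 1 is to "Determine the correlation of SpiroPD handheld spirometry measurements with bedside Koko spirometry lung function". Statistical Analyses, SA1, states: "Correlation between KoKo and SpiroPD measurements will be assessed using Spearman's correlation coefficient". Both SA1 and the Methods Overview treat a coefficient above 0.8 as showing that the device is useful.

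The data for a comparison of change are already scheduled. The Methods Overview says "Participants will complete comparative lung function measurements with both devices while in the hospital or clinic at time of enrollment and at the 30-day follow" …, and the Study Schema lists spirometry at baseline and at 30 days. No section plans an analysis of change between the visits, a within-patient correlation, or agreement of changes. SA2 covers adherence, exacerbations, utilization and patient characteristics.

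**The concern.** A correlation of levels across patients asks whether the two devices rank patients alike. Monitoring asks something else: when one patient's lung function moves, does SpiroPD move with it by about the right amount? The inclusion criteria admit any adult with physician-diagnosed COPD, from hospital and clinic, so the spread between patients is probably wide. A wide spread lifts the correlation of levels whatever happens within a patient.

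At stake is what the pilot may claim. A result above 0.8 could be read as support for following response to therapy when SpiroPD's error is as large as the changes of interest. The Background says that the pilot will prepare further studies and grant applications, so such a reading would carry forward.

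**Working it through.** **The plan's own figure.** The sample-size table gives N = 145.92 for a correlation of 0.23, 80% power and alpha 0.05. Fisher's z, two-sided: n = ((1.960 + 0.842)/atanh(0.23))² + 3 = (2.802/0.2342)² + 3 ≈ 146.1. This reproduces. It is the size for testing a correlation against zero; it addresses neither the 0.8 threshold nor change.

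**Inputs.** From the documents: 150 participants, both devices at enrollment and day 30, threshold 0.8. Not in the documents, so assumed:
- between-patient FEV1 SD, B: 0.5 L (0.4-0.6)
- SD of true 30-day change, C: 0.15 L (0.10-0.20)
- KoKo error SD, K: 0.07 L
- SpiroPD error SD, S: 0.15 L (0.10-0.20)

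Errors are independent, distributions normal, and true change is independent of baseline. Spearman = (6/π)·asin(r/2), where r is the Pearson correlation.

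**Case 1: SpiroPD follows change fully but is noisy (S equal to C).**
- Baseline levels: r = B²/√((B²+K²)(B²+S²)) = 0.25/√(0.2549 × 0.2725) = 0.949; Spearman 0.94.
- Day-30 levels: r = 0.2725/√(0.2774 × 0.2950) = 0.953; Spearman 0.95.
- Changes: r = C²/√((C²+2K²)(C²+2S²)) = 0.0225/√(0.0323 × 0.0675) = 0.482; Spearman 0.46.
- Over the assumed ranges: levels 0.87-0.98, changes 0.23-0.72.

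**Case 2: SpiroPD registers none of the change.**
- Day-30 levels: r = B²/√((B²+C²+K²)(B²+S²)) = 0.25/√(0.2774 × 0.2725) = 0.909; Spearman 0.90.
- Over the assumed ranges: 0.78-0.96. The correlation of changes is 0.

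**Case 2 with larger change.** Simulation with n = 150, mean change 0.1 L and error SD 0.1 L for both devices, 400 replicates per setting, device blind to change. The last three columns are for between-patient SD 0.4, 0.5 and 0.6 L.

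| Change SD | Result at day 30 | 0.4 L | 0.5 L | 0.6 L |
|---|---|---|---|---|
| 0.20 L | mean Spearman | 0.83 | 0.88 | 0.91 |
| | share above 0.8 | 85% | 100% | 100% |
| 0.30 L | mean Spearman | 0.74 | 0.81 | 0.86 |
| | share above 0.8 | 8% | 68% | 99% |
| 0.40 L | mean Spearman | 0.65 | 0.74 | 0.80 |
| | share above 0.8 | 0% | 5% | 51% |

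The baseline correlation was 0.93-0.97 in all these settings and always passed, as it must, because no change has yet occurred.

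**Can the change data separate the devices?** At between-patient SD 0.5 L, change SD 0.20 L and error SD 0.1 L, the Spearman of changes is about 0.00 for the blind device and 0.65 for one that follows change fully. With 75 pairs, the 95% interval is about ±0.23 around 0, and 0.43-0.73 around 0.6. With 150 pairs it is ±0.16, and 0.48-0.70.

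**What agreement of changes would show.** In the central Case 1, the SD of the difference in change is √(2(K²+S²)) = √(2 × 0.0274) = 0.234 L. Limits of agreement are ±1.96 × 0.234 = ±0.46 L around the mean difference, against an assumed change SD of 0.15 L. With 75 pairs the mean difference has a 95% interval of about ±1.96 × 0.234/√75 = ±0.05 L.

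**The case against.** **The blind device is contrived.** No mechanism is offered by which a spirometer would return last month's value plus noise, and the Methods Overview describes the device as FDA-cleared and used as intended. This stands: Case 2 is a limiting case that shows what the criterion cannot detect. Case 1, ordinary random error, is the realistic one.

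**A reader might infer that a device missing change is bound to pass.** The documents do not support that. SA1 does not say which visit it uses or whether visits are pooled. A pass is assured only at baseline; at day 30 the blind device can fall below 0.8 when change is large relative to the spread between patients.

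**Agreement on levels would expose the noise.** With independent errors, the SD of the difference in change is √2 times that of the level difference (0.234 L against √0.0274 = 0.166 L). That is correct, but the plan contains no agreement analysis on levels either. Change also tells more when a patient's errors are correlated across visits, which this model omits.

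**A reader might infer that the 30-day course is wasted, or that inpatients must improve across it.** Neither holds. SA2 uses the month for adherence and utilization, day-30 spirometry may enter SA1, and the daily home readings bear on SpiroPD's repeatability, although they have no KoKo partner. The Background speaks of responses to therapy. The inclusion criteria admit inpatients hospitalized for reasons other than COPD, and inpatient testing starts no earlier than day 2. Only the paired change is left unanalysed.

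**It is a pilot, and its central hypothesis concerns determining lung function.** This limits the weight of the point but does not remove it, because the plan itself turns the coefficient into a statement of usefulness.

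**Conclusion.** The concern holds in this form: the stated use is longitudinal, the only device criterion is a correlation of measurements, and a result above 0.8 could come from a device that follows change poorly. Under the assumed SDs, levels correlate at 0.87-0.98 while changes correlate at 0.23-0.72, and a change-blind device gives 0.78-0.96 at day 30, lower with larger true change. Every SD is an assumption. That SA1 means levels is the plain reading, and FEV1 is chosen here because SA1 names no parameter.

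Two stronger readings are not supported. Nothing in the documents shows that SpiroPD fails to follow change. Nor would a low correlation of changes show it: in Case 1 the device follows change fully and still scores only 0.23-0.72, so the 0.8 cut-off cannot be carried over. The point should be acted on, but it does not invalidate SA1 as a single-occasion comparison.

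**What to change.** Add to SA1, for participants with both devices at both visits, the agreement of the day-30-minus-baseline change in FEV1:
- the mean and SD of the SpiroPD-minus-KoKo difference in change, with limits of agreement and 95% confidence intervals;
- results overall and separately for inpatient and clinic enrollees;
- the correlation of changes as a descriptive figure only, with no 0.8 cut-off.

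State that a coefficient above 0.8 on levels supports single-occasion ranking of patients only, and that any statement about monitoring response to therapy rests on the agreement of changes.

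The cost is SAP wording and one analysis of data already scheduled. There are two downsides. Participants followed up by phone have no day-30 KoKo value and contribute no pair. The documents give no expected proportion, and those absent may differ from those who attend, so report the number of pairs and compare participants with and without them. The conclusion may also be less favourable than the correlation of levels.
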